BIOMICROSCOPIC SLIT-LAMP EXAM

A biomicroscopic slit-lamp exam must be performed at each postoperative visit to determine the presence or absence of any medical or lens findings, complications or adverse events. IOL decentration and tilt are to be determined subjectively. The center of the lens relative to the pupil can be used to determine IOL decentration. The diffractive rings of Symfony lens can be used as a guide to locate the center of the IOL. Note that the pupil center may not always be aligned with the visual axis of the eye; therefore, the investigator should consider deviations in pupil center from visual axis when reporting IOL decentration.

ND:YAG CAPSULOTOMY

If an Nd:YAG capsulotomy is necessary, it is recommended that the procedure be performed after study completion.

MEIBOMIAN GLAND ASSESSMENT

Meibomian glands assessment is to be measured at the designated postoperative visits. The method of the assessment is described in **Appendix G**.

FUNDUS EXAM

A dilated fundus exam will be done preoperatively and may be performed postoperatively at the investigator's discretion. Examinations may be done dilated with ophthalmoscopy or undilated with any imaging system that allows for undilated views of peripheral retina (e.g., Optomap). The same fundus exam method that was used for preoperatively should be used postoperatively if the exam is performed.

MEIBOMIAN GLAND IMAGING (LIPISCAN/LIPIVIEW II)

Meibomian gland imaging will be captured through LipiScan or LipiView II at the designated visits, to capture Meibomian gland images of both eyes and grade eyelids, as shown in **Appendix I**. Refer to the LipiView Interferometer and LipiScan Instructions for Use for detailed instructions on the device operation. For subjects in Control group, both eyes will be measured at 4-month visit as well. It is recommended that the same methods be used for all study subjects at the site for the duration of the study.

**STANDARD PATIENT EVALUATION OF EYE DRYNESS (SPEED)
QUESTIONNAIRE**

The SPEED questionnaire will be administered at the beginning of any designated visits, prior to any visual acuity testing.

**OCULAR / VISUAL SYMPTOMS ASSESSMENT (NON-DIRECTED;
SPONTANEOUS)**

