10.7 EXIT OF SUBJECTS

An Exit Case Report Form will be completed for all subjects, either when they complete the study or if they exit early.

It is the responsibility of the investigator to provide complete follow-up data to JJSV for each subject, and every attempt should be made to gather that complete follow-up data for all subjects enrolled as missing data can have a negative effect on the study results. Patients who will be traveling, relocating or otherwise unavailable for postoperative follow-up visits should not be chosen for this clinical study.

A subject will be considered a “screen failure” if he/she does not meet the inclusion/exclusion criteria or if consent is withdrawn prior to randomization.

A subject will be considered “discontinued prior to treatment” if the subject is randomized but does not undergo bilateral LipiFlow treatment (study group) or receive a Symfony lens for various reasons including: the planned implant being aborted due to surgical complications, the subject withdrawing consent prior to treatment, or the subject died prior to treatment. If a subject receives at least one Symfony lens, he/she is to be followed according to the protocol.

A subject will be “discontinued” from the study if one study lens (if implanted unilaterally) or both study lenses (if implanted bilaterally) are removed or if the subject dies.

Subjects will be considered “lost-to-follow-up” from the study only if irretrievably lost for unavoidable reasons such as: subject moved/unable to locate, subject uncooperative/refuses further study participation, subject ill/unable to travel. In the event of subject relocation, efforts must be made by the investigator to secure follow-up information (i.e., slit-lamp findings and general visual acuity, etc.) from the subject’s new physician.

If a subject is exited early from the study, the investigator will send an Exit Case Report Form to JJSV indicating the reason for study exit. In the event of a lens removal or other serious adverse event, the subject may be exited from the study; however, efforts must be made by the investigator to follow the subject until resolution of the adverse event.

Following study completion or early exit, all study subjects are to be instructed to undergo regular eye examinations at least yearly and also to return to their doctor if any eye complications are experienced in the interim.

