10.8 UNSCHEDULED VISITS

During the study period, if a non-protocol-required visit is done for the purpose of medically-indicated follow-up for a study eye, data from this visit should be reported using the Unscheduled Visit CRF. The need for unscheduled visits is at the investigator’s discretion. Specific examinations to be performed at unscheduled visits are also at the discretion of the investigator (based on the reason for the unscheduled visit) and data are to be recorded in the appropriate section of the case report form.

Data to be collected may include:

- UCDVA and BCDVA
- Manifest refraction
- Biomicroscopic slit-lamp examination for medical and/or lens findings
- Fundus exam
- Ocular symptoms
- Adverse events
- Ocular and systemic medications

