11. ADVERSE EVENTS AND PRODUCT COMPLAINTS

11.1 ADVERSE EVENT DEFINITIONS

Adverse Event (AE)

An adverse event is defined (following ISO 14155) as any untoward medical occurrence, unintended disease or injury, or untoward clinical signs (including abnormal laboratory findings) in subjects, users or other persons, whether or not related to the study device.

Serious Adverse Event (SAE)

An adverse event is considered serious (following ISO 14155) if it is an untoward occurrence which may or may not be related to use of the study device that

- is sight- or life-threatening,
- results in death,
- requires inpatient hospitalization or prolongation of hospitalization (a planned hospitalization for a pre-existing condition without a serious deterioration in health is not considered a serious adverse event),

- results in permanent impairment of a body structure or body function,
- necessitates medical or surgical intervention to prevent permanent impairment to a body structure or function, or
- results in fetal distress, fetal death or a congenital abnormality or birth defect

Device-Related Adverse Event/Adverse Device Effect (ADE)

A device-related adverse event is defined as any adverse even that is believed to be definitely, probably or possibly related to the study device (following the guidelines in Section 11.4, Causal Relationship). A device-related event is also considered an adverse device effect (ADE; following ISO 14155) resulting from the use of the study device that may result from user error, insufficiencies or inadequacies in the instructions for use, deployment, implantation, installation, operation of any malfunction of the device.

Study-Specific Serious Anticipated Adverse Events

The following is a list including, but not limited to, ocular serious adverse events that are anticipated and must be reported to JJSV for this study. Adverse event definitions in accordance with the American Academy of Ophthalmology Task Force Consensus Statement are included in **Appendix U**.

- Endophthalmitis/Intraocular infection
- Hypopyon
- Hyphema
- IOL dislocation
- Cystoid macular edema
- Pupillary block
- Retinal detachment/tear
- Persistent corneal edema
- Persistent iritis
- Persistent uveitis
- Persistent raised IOP requiring treatment
- Toxic anterior segment syndrome
- Visual symptoms requiring secondary surgical intervention (e.g., lens removal)
- Tilt and decentration requiring secondary surgical intervention (e.g., repositioning)

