- Residual refractive error resulting in a secondary surgical intervention
- Retained lens material resulting in secondary surgical intervention

NOTE 1: Wound burps during the first week postoperatively, suture removal, planned blepharoplasty and Nd:YAG capsulotomy (for PCO) are not considered adverse events for this study.

NOTE 2: Persistent corneal edema, IOP increase, and uveitis/iritis will be considered serious according to the guidelines listed in **Appendix U**. (i.e., persistent IOP increase of 10 mm Hg from baseline to at least 25 mm Hg; corneal edema resulting in BCDVA of 20/40 or worse at 1 month or later; and Grade 1+ uveitis/iritis longer than 3 months.

Unanticipated Adverse Device Effect (UADE)/Unanticipated Serious Adverse Device Effect (USADE)

Any UADE (USA 21CFR 812.3(s)) or USADE (ISO 14155) is defined as any serious adverse effect on health or safety or any life-threatening problem or death caused by, or associated with, a device, if that effect, problem, or death was not previously identified in nature, severity, or degree of incidence in the investigational plan (i.e., this protocol), application (including a supplementary plan or application), or risk assessment, or any other unanticipated serious problem associated with a device that relates to the rights, safety, or welfare of subjects.

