#### 2 ANALYSIS POPULATIONS

#### 2.1 ANALYSIS POPULATIONS

The primary analysis population will be all eyes that are randomized for the precision of biometric measurements, and all eyes that are randomized and implanted for all other analyses. Mean change in total Meibomian gland score will be compared between study group eyes and control group eyes at 1 month postoperatively. All other key study endpoints will be evaluated at 3 months postoperatively. Additional endpoints will be evaluated at 1 month and 3 months postoperatively for the study group and control group and 4 months postoperatively for crossover control group only. Missing data will not be imputed.

Since both eyes of the same subject will be randomized into the same group, eye-specific measurements of same subject are clustered and likely to be positively correlated. As a subset analysis, right and left eyes of subjects will be analyzed for the key eye-specific study endpoints separately to assess for any differences by eye. Demographics/enrollment/accountability data and binocular data will be reported for all randomized subjects with study IOLs successfully implanted.

Version 1.0 1 SAP/DRYE-102-SELF

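### Neither document says how an eye with secondary lens surgery before Month 3 enters the predictability, UCDVA and symptom endpoints

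*Protocol*

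**What the plan says.** - **Anticipated events.** Protocol 11.1 lists among its serious anticipated events "Residual refractive error resulting in a secondary surgical intervention" and "Visual symptoms requiring secondary surgical intervention (e.g., lens removal"). It also lists tilt or decentration that leads to surgery such as repositioning.
- **Exit.** Protocol 10.7 discontinues a subject "if one study lens (if implanted unilaterally) or both study lenses (if implanted bilaterally) are removed or if the subject dies". It then adds: "In the event of a lens removal or other serious adverse event, the subject may be exited from the study".
- **Population and missing data.** For the postoperative endpoints SAP 2.1 analyses "all eyes that are randomized and implanted for all other analyses", and states "Missing data will not be imputed". Protocol 20.1 agrees on both.
- **Endpoints.** SAP 4.1.1 (mean monocular UCDVA), 4.1.3 (MRSE within 0.50 D and 1.00 D of target) and 4.1.4 (moderate or severe symptoms) are evaluated at 3 months. None mentions a secondary intervention.
- **Other procedures.** Protocol 10.6 NOTE 1 bars additional refractive procedures, naming limbal relaxing incisions, PRK, LASIK and LASEK. On capsulotomy, 10.6 says: "If an Nd:YAG capsulotomy is necessary, it is recommended that the procedure be performed after study completion". Under 11.1 NOTE 1, capsulotomy for posterior capsule opacification is not an adverse event.
- **Data available beforehand.** Appendix B schedules monocular UCDVA and manifest refraction at Month 1. It schedules no PRVSQ at Month 1, although Appendix D places that questionnaire at every follow-up visit. Protocol 10.8 says: "Specific examinations to be performed at unscheduled visits are also at the discretion of the investigator".

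**The concern.** The hypothesis in Protocol 3 is that LipiFlow makes biometry more precise and so improves refractive predictability, vision and comfort. An eye re-operated because its refraction missed target is the plainest failure on predictability. A subject whose lens is removed for visual symptoms is the plainest failure on symptoms. If such cases leave the denominators, or appear only after correction, each arm looks better than its original surgery was. Their absence is informative, because the outcome itself led to the missing or altered value.

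The study is open-label and exit after a lens removal is partly discretionary. A rule chosen once the data are visible would be post hoc.

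**Working it through.** **1. What happens by default.**

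- *Sole lens or both lenses removed:* the subject is discontinued (10.7). With no Month 3 data and no imputation, the case leaves all three analyses.
- *One of two lenses removed:* exit is optional. If the subject stays, no sentence says whether that eye's later data count. The eye still belongs to the implanted population, which points to inclusion. Protocol 10.6 NOTE 3 treats a fellow eye that never received a study lens as exited, which points the other way.
- *Lens exchanged or repositioned:* Appendix U separates these from removal, and the eye keeps a study lens. Nothing triggers exit, so the post-intervention value is the one available at Month 3.
- *Corneal enhancement:* barred by 10.6 NOTE 1, so it would be a protocol deviation. The remaining route is lens surgery, up to the Month 3 visit at 10 to 14 weeks after second-eye surgery.

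**2. The plan's own figure, used only as a yardstick.** SAP 5 assumes 55 evaluable subjects per arm, SD 1.6 lines, a 1-line effect and one-sided alpha 0.05.

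- Enrolment: 55/(1 - 0.20) = 68.75, rounded up to 69, as stated.
- Power by the noncentral t distribution: 94.7%, which agrees with the SAP's claim of over 90%.
- With 1 line = 0.1 LogMAR, the smallest significant difference at subject level is 1.659 x 0.16 x sqrt(2/55) = 0.051 LogMAR.

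**3. Predictability within one arm.** Let *q* be the share of eyes re-intervened before Month 3 and *p* the share of the other eyes within 0.50 D. The documents give neither, so both are assumed. The rate is *p* if the re-intervened eyes are dropped, *p*(1 - *q*) + *q* if all are in range after correction, and *p*(1 - *q*) if they count as failures.

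| *q* | *p* | dropped | all in range after correction | counted as failures |
|---|---|---|---|---|
| 0% | 80% / 90% | 80.0% / 90.0% | 80.0% / 90.0% | 80.0% / 90.0% |
| 1% | 80% / 90% | 80.0% / 90.0% | 80.2% / 90.1% | 79.2% / 89.1% |
| 3% | 80% / 90% | 80.0% / 90.0% | 80.6% / 90.3% | 77.6% / 87.3% |

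The widest gap between rules equals *q*, so 0 to 3 points. In counts, take 110 eyes per arm (2 x 55), two of them re-intervened, and 99 of the other 108 in range. The rates are 99/108 = 91.7%, 101/110 = 91.8% and 99/110 = 90.0%.

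**4. Between arms (Study minus Control, 110 eyes each, same *p* in both).**

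- *3 Control eyes and 1 Study eye re-intervened:* 0 points if dropped, -0.4 (*p* = 80%) or -0.2 (*p* = 90%) if all are in range after correction, and +1.5 or +1.6 if counted as failures.
- *1 Control and 3 Study:* the same values with signs reversed.
- *3 in each arm:* 0 under every rule. If *p* differs by arm while *q* is equal, the two rules that keep the eyes only scale the difference by 1 - *q*. For example, 10 points become 9.7 at *q* = 3%.

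**5. UCDVA.** Take two of 110 eyes at an assumed 0.70 LogMAR before surgery and the rest averaging an assumed 0.05. Using the pre-intervention values raises the arm mean by 2 x (0.70 - 0.05)/110 = 0.012 LogMAR, or 0.12 line. That is 0.012/0.051, about a quarter of the smallest significant difference. With *q* = 1-3% and eyes 3-5 lines worse before surgery, the shift runs from 0.01 x 3 = 0.03 to 0.03 x 5 = 0.15 line.

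**6. Symptoms.** This endpoint counts subjects. One subject among 55 changes the rate by at most 1/55 = 1.8 points. Because Appendix B has no Month 1 PRVSQ, a subject who exits early may have no postoperative directed-symptom score at all.

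**The case against.** The strongest reply is that the point rests on silence, on assumed numbers and on small effects.

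- **The events are visible elsewhere.** SAP 4.2.4 tabulates adverse events by group, and SAP 3.1 and Appendix I report discontinuations by group. This is true, but those tables do not alter the endpoint estimates, and capsulotomy for posterior capsule opacification need not appear in the adverse event table.
- **The effect is small.** A shift of 1.7-1.8 points is below one standard error of a 90% rate in 110 eyes: sqrt(0.9 x 0.1/110) = 2.9 points, ignoring the pairing of eyes. Predictability has no success criterion. This stands and limits the weight of the point.
- **Any bias is conservative.** This holds only if the affected eyes are mainly in Control. If they are mainly in Study, the default hides a harm.
- **A last pre-intervention value mixes time points.** It would put Month 1 acuity into a Month 3 mean. This stands, so that approach belongs in a sensitivity analysis.

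A reader might also infer more than the documents support:

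- *That the plan counts corrected eyes as successes.* No sentence says so, and a corrected eye may still miss target.
- *That the worst failures are always hidden and the comparison is always pulled toward no difference.* That requires rates that differ by arm.
- *That repositioning for tilt or decentration, or an early capsulotomy, is a failure of LipiFlow.* Nothing in Protocol 3 links lens position or capsule opacity to the treatment.
- *That surgeons who know the arm will intervene differently.* The open-label design permits this, but nothing in the documents shows it.

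**Conclusion.** The gap is real and modest in size. Protocol 11.1 anticipates lens surgery for two outcomes that the trial measures, yet neither document assigns these cases a place in the Month 3 endpoints. The default is to drop those who exit and possibly to analyse those who stay at a post-intervention value.

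At an assumed 0-3% of eyes, the choice of rule moves an arm's predictability rate by about 0-3 points. Over the non-zero part of that range, mean UCDVA moves by roughly 0.03-0.15 line against a 1-line design effect. These sizes rest on assumed re-intervention rates, pre-intervention acuities and predictability among the other eyes. The bar on corneal procedures and the short follow-up both point to the low end. The gap is worth closing because it is cheap to do before database lock and cannot be done credibly afterwards.

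**What to change.** 1. **SAP 4.1.3:** an eye whose study lens is removed or exchanged for residual refractive error before Month 3 counts as outside both 0.50 D and 1.00 D.
2. **SAP 4.1.4:** a subject with lens removal for visual symptoms before Month 3 counts as having bothersome symptoms.
3. **Reporting:** give the number of secondary interventions, by reason, and of Nd:YAG capsulotomies before Month 3, by arm. Repositioned eyes and eyes with capsulotomy otherwise stay as observed.
4. **SAP 4.1.1:** keep as-observed UCDVA as the primary analysis. Add a sensitivity analysis that uses the last available postoperative value before a secondary intervention, for example Month 1, which Appendix B already collects. Report how many eyes have no such value.
5. **Reconcile Protocol 10.6 NOTE 1 with the 11.1 entry on refractive re-intervention**, so that it is clear which events the analysis rules cover.

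The cost is SAP wording and one extra table. No subjects, visits or tests are added, and nothing changes about when or whether a procedure or an unscheduled examination is performed. The downside is that reported success rates may be slightly less favourable.

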10.8 UNSCHEDULED VISITS

During the study period, if a non-protocol-required visit is done for the purpose of medically-indicated follow-up for a study eye, data from this visit should be reported using the Unscheduled Visit CRF. The need for unscheduled visits is at the investigator’s discretion. Specific examinations to be performed at unscheduled visits are also at the discretion of the investigator (based on the reason for the unscheduled visit) and data are to be recorded in the appropriate section of the case report form.

Data to be collected may include:

- UCDVA and BCDVA
- Manifest refraction
- Biomicroscopic slit-lamp examination for medical and/or lens findings
- Fundus exam
- Ocular symptoms
- Adverse events
- Ocular and systemic medications

10.9 PROTOCOL DEVIATIONS

Any departure from the protocol procedures represents a protocol deviation. Protocol deviations may be subject-based (e.g., inclusion/exclusion criteria, informed consent deviation, etc.) or procedural-based (e.g., out-of-interval visits, non-compliance with testing procedures, etc.). All protocol deviations will be documented using protocol deviation case report forms. Any deviation made to protect the life or physical well-being of a subject in an emergency as well as any use of the investigational device without obtaining informed consent must be reported to JJSV within 5 working days. Protocol deviations will be monitored by JJSV, and if the non-compliance is persistent or egregious, JJSV may take action, including but not limited to termination of the investigator's participation in the study. The investigator is also responsible for informing the reviewing IRB of instances of protocol non-compliance in accordance with the IRB requirements.

11. ADVERSE EVENTS AND PRODUCT COMPLAINTS

11.1 ADVERSE EVENT DEFINITIONS

Adverse Event (AE)

An adverse event is defined (following ISO 14155) as any untoward medical occurrence, unintended disease or injury, or untoward clinical signs (including abnormal laboratory findings) in subjects, users or other persons, whether or not related to the study device.

Serious Adverse Event (SAE)

An adverse event is considered serious (following ISO 14155) if it is an untoward occurrence which may or may not be related to use of the study device that

- is sight- or life-threatening,
- results in death,
- requires inpatient hospitalization or prolongation of hospitalization (a planned hospitalization for a pre-existing condition without a serious deterioration in health is not considered a serious adverse event),

- results in permanent impairment of a body structure or body function,
- necessitates medical or surgical intervention to prevent permanent impairment to a body structure or function, or
- results in fetal distress, fetal death or a congenital abnormality or birth defect

Device-Related Adverse Event/Adverse Device Effect (ADE)

A device-related adverse event is defined as any adverse even that is believed to be definitely, probably or possibly related to the study device (following the guidelines in Section 11.4, Causal Relationship). A device-related event is also considered an adverse device effect (ADE; following ISO 14155) resulting from the use of the study device that may result from user error, insufficiencies or inadequacies in the instructions for use, deployment, implantation, installation, operation of any malfunction of the device.

Study-Specific Serious Anticipated Adverse Events

The following is a list including, but not limited to, ocular serious adverse events that are anticipated and must be reported to JJSV for this study. Adverse event definitions in accordance with the American Academy of Ophthalmology Task Force Consensus Statement are included in **Appendix U**.

- Endophthalmitis/Intraocular infection
- Hypopyon
- Hyphema
- IOL dislocation
- Cystoid macular edema
- Pupillary block
- Retinal detachment/tear
- Persistent corneal edema
- Persistent iritis
- Persistent uveitis
- Persistent raised IOP requiring treatment
- Toxic anterior segment syndrome
- Visual symptoms requiring secondary surgical intervention (e.g., lens removal)
- Tilt and decentration requiring secondary surgical intervention (e.g., repositioning)
- Residual refractive error resulting in a secondary surgical intervention
- Retained lens material resulting in secondary surgical intervention

NOTE 1: Wound burps during the first week postoperatively, suture removal, planned blepharoplasty and Nd:YAG capsulotomy (for PCO) are not considered adverse events for this study.

NOTE 2: Persistent corneal edema, IOP increase, and uveitis/iritis will be considered serious according to the guidelines listed in **Appendix U**. (i.e., persistent IOP increase of 10 mm Hg from baseline to at least 25 mm Hg; corneal edema resulting in BCDVA of 20/40 or worse at 1 month or later; and Grade 1+ uveitis/iritis longer than 3 months.

Unanticipated Adverse Device Effect (UADE)/Unanticipated Serious Adverse Device Effect (USADE)

Any UADE (USA 21CFR 812.3(s)) or USADE (ISO 14155) is defined as any serious adverse effect on health or safety or any life-threatening problem or death caused by, or associated with, a device, if that effect, problem, or death was not previously identified in nature, severity, or degree of incidence in the investigational plan (i.e., this protocol), application (including a supplementary plan or application), or risk assessment, or any other unanticipated serious problem associated with a device that relates to the rights, safety, or welfare of subjects.

